Weight change over dry weight? (y/n or drop down)

- ≥ 5 lbs
- 1-4 lbs
- At or below dry weight

(Any Symptom + ≥ 5 lbs weight change over dry weight)

Diuretic Medication? (y/n)

- Are you on the same (standard) diuretic dose you were placed on at discharge or by your heart failure physician after an outpatient appointment?

(If on same medication and either new symptoms of shortness of breath at rest, lower extremity edema, orthopnea, PND or ≥ 5 lbs weight gain or 1-4 lbs weight gain with a prespecified number of standard alerts or a high risk alert than ask patient to double diuretic dose)

(If on double diuretic dose and no longer symptomatic AND back to dry weight, deescalate diuretic dose to discharge dose)

If you had symptoms yesterday are your symptoms better, worse, or the same today? (drop down for 4 choices: better, worse, same, N/A)

(If worse phone call to care team)

Med adherence? (y/n)

- Have you missed any diuretic doses in last 24h
- Have you missed any medication doses in last 24h

(Any symptom + not adherent to any meds) Reinforce importance of med adherence

Changes in diet, Salt intake? (y/n)

- Are you eating meals that you are making at home?

(Any symptoms + not eating meals that you are making at home) Reinforce importance of low salt diet and eating meals that you are making at home

Alerts over last 24 hours

- Was a high risk alert triggered (y/n)
- How many high risk alerts triggered: (Numerical answer)
- Were any standard alerts triggered (y/n)
- How many standard alerts triggered: (Numerical answer)

(High risk alert triggered)**Plan: (Multiple choice)**

- a. Phone call to clinical team for concerning symptoms
- b. Escalate or double diuretic dose
- c. Deescalate diuretic dose
- d. Reinforce med adherence
- e. Reinforce dietary adherence
- f. Other (free text)

Table 2: Phase 1, monitoring nurse nurse alerts system for clinical team for CHF

Table 2 will be configured into a note template within EPIC that allows for data elements to be captured. If any of the black or red bold logic is met the note will be forwarded to the clinical team with a high priority. If any of the red bolded elements are elicited from the patient, then the monitoring nurse will call the CHF clinical team for immediate communication. All notes will be forwarded to the clinical care team.

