In addition, the monitoring nurse will double the diuretic dosing if a patient has new symptoms of shortness of breath at rest, orthopnea, postural nocturnal dyspnea, or lower extremity swelling. The double diuretic dosing will also occur if weight gain increases by ≥ 5 lbs over dry weight. If the symptom question is met, then the patient will get a 3rd question on Day n+1 that asks if the symptoms are getting better, worse or the same. If the symptoms are getting worse, the monitoring nurse will escalate to the clinical care team with a phone call. If the symptoms are getting better or are the same, the double dose of diuretic will remain unchanged. If symptoms or weight gain normalize, the double dose of diuretic will be deescalated to the standard dosing regimen.

If there is a high-risk alert, then the monitoring nurse receives an alert, which will result in a phone call to the patients and note template with patients. The monitoring nurse alert will also occur if there are a certain number of alerts (to be determined and varied during patients 1-5) and 1-4 lbs of weight gain (to be determined and varied during patients 1-5). In addition, if patients have some combination of weight gain and standard alerts or a high-risk alert, then the doubling of diuretics will also occur. If patients have a combination of 1-4 lb weight gain and a set number of device alerts, we will stop diuretic dosing if weight gain normalizes back to dry weight. The process map for patients 1-5 is shown in Figure 1. Escalating and deescalating diuretic dosing will also be built into the same note template in addition to prompts for education to ensure a standardized process from the monitoring nurses. We also have a multiple-choice option for monitoring nurse to document the care plan for participants.

[figure not shown]

Figure 1: Process map for CHF Patient 1-5

If care is escalated to the clinical care team which includes Advanced Practice Nurses, Physician Assistants and Physicians, the care team will pursue various interventions including counseling, altering medication therapy, urgent visits to heart failure clinic ideally within 72 hours, and if no other available options readmission. These workflows will be left to the discretion of the clinical care team given the nuance in taking care of these high-risk patients and the existing relationship and prior history with

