Plan 
 3. Plan? Please select all that apply from the following options (multi-select) 
 a. Continue PO diuretic

- b. Increase PO diuretic
- c. Decrease PO diuretic
- d. Hold PO diuretic
- e. Start IV diuretic
- f. Was there a change or new addition of a BB
- g. Was there a change or new addition of a ACEI/ARB/ARNI
- h. Was there a change or new addition of mineralocorticoid receptor antagonists (MRAs)
- i. Start antibiotic
- j. Start breathing treatment

Other interventions (not medication related)

- a. Have monitoring nurse do in person visit
- b. Set up cardiology urgent visit
- c. Send patient to the ER
- d. Check labs
- e. Check imaging
- f. Other (free text)

Table 3. Mid-level CHF Note Template

For phase 1 and 2 there will be significant data collection that is part of this process to understand how our process maps result in outcomes. Learnings from these 20 patients will inform the final process for phase 3 CHF.

QUALITATIVE

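### Table 2 doubles the patient's current standard diuretic dose but steps it down to the discharge dose, which is out of date if the dose was raised after discharge

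*Protocol*

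**What the plan says.** All of this is in Protocol section 2.2, Experimental Plan and Methods.

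- **Starting dose (Table 2, diuretic item).** The nurse asks: "Are you on the same (standard) diuretic dose you were placed on at discharge or by your heart failure physician after an outpatient appointment". The standard dose can therefore come from discharge or from a later outpatient decision.
- **Escalation (same item).** If the patient is on that dose and a symptom, weight or alert trigger is met, the nurse is "than ask patient to double diuretic dose".
- **Step-down (same item).** "If on double diuretic dose and no longer symptomatic AND back to dry weight, deescalate diuretic dose to discharge dose".
- **Step-down (narrative after Table 2).** When symptoms or weight normalise, "the double dose of diuretic will be deescalated to the standard dosing regimen".
- **Changes after discharge.** Once a case is escalated, "the clinical care team which includes Advanced Practice Nurses, Physician Assistants and Physicians" may act, and the listed actions include "altering medication therapy, urgent visits to heart failure clinic ideally within 72 hours". Table 3, the mid-level note template, offers "Increase PO diuretic" as a plan option.
- **Use.** "Table 2 will be configured into a note template within EPIC". The narrative adds that dose escalation and de-escalation will be built into that same template so that the monitoring nurses work in a standard way.

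**The concern.** The starting dose for doubling has two possible sources and the return dose has one. They coincide while the maintenance dose stays as it was at discharge. They separate once a clinician raises it, which the protocol foresees.

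A nurse who then follows the step-down line as written takes the patient past the current maintenance dose to an older, lower one. This would happen just after an episode that triggered doubling, in a patient whose clinician had already moved away from the discharge dose. The matter is the correctness of a dosing instruction in high-risk heart failure patients. It does not bear on an endpoint or analysis.

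**Working it through.** The protocol gives no figure to reproduce here. The check compares the rules and then traces the dose.

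**Rules side by side**

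| Step | Where | Dose named |
|---|---|---|
| Starting dose | Table 2, diuretic question | Set at discharge, or later by the heart failure physician |
| Doubling | Table 2, next line | Twice the starting dose |
| Step-down | Table 2, following line | Discharge dose only |
| Step-down | Narrative after Table 2 | Standard regimen |

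The Table 2 question attaches the word standard to both sources of the dose. The narrative's standard regimen therefore fits the starting dose, and the Table 2 step-down line does not. No other text shown says that the discharge dose means the dose currently in force.

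**Tracing the dose**

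Let D be the discharge dose and kD the maintenance dose after a post-discharge raise, with k > 1. The protocol gives no value of k, so those below are assumptions.

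- Doubled dose: 2 × kD = 2kD.
- Step-down target in Table 2: D.
- Step-down target in the narrative: kD.
- Share of the maintenance dose left under Table 2: D / kD = 1/k.
- Cut from the doubled dose under Table 2: 1 − D/(2kD) = 1 − 1/(2k). Under the narrative it is 1 − kD/(2kD) = 50%.

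| k (assumed) | Doubled dose | Table 2 target | Narrative target | Share of maintenance dose left | Cut under Table 2 |
|---|---|---|---|---|---|
| 1 (no change) | 2D | D | D | 1/1 = 100% | 1 − 1/2 = 50% |
| 1.5 | 3D | D | 1.5D | 1/1.5 = 67% | 1 − 1/3 = 66.7% |
| 2 | 4D | D | 2D | 1/2 = 50% | 1 − 1/4 = 75% |

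With k = 1 the rules agree. With any k > 1 the Table 2 line leaves the patient below the maintenance dose.

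**How many patients**

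Table 2 is labelled Phase 1, and section 2.2 gives Phase 1 five patients, so 5 is the ceiling. A patient is affected only if three things happen in order: the maintenance dose is raised after discharge, the nurse later doubles from that new dose, and symptoms then resolve with return to dry weight. The protocol gives no rate for any of these, so the expected number cannot be derived and may be zero.

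**The case against.** The case against has five parts.

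- **Shorthand.** The discharge dose may simply be a short name for the usual case, and the narrative's wording shows the sensible reading. That is probably the intent. But the same Table 2 item lists discharge and outpatient dosing as alternatives, so a user has no signal that one now stands for both.
- **Narrower route.** The Table 2 question recognises only a dose set at discharge or by the heart failure physician after an appointment. Read strictly, a raise made by a mid-level provider is not a standard dose, so Table 2 would not double from it. Table 3 also does not say whether its increase option is a lasting or a temporary change. This weakens Table 3 as evidence but leaves the conflict in place. The physician route is named in Table 2 itself, and the narrative has the nurse double on symptoms or weight without limiting who set the prior dose.
- **Template and figure not seen.** The built EPIC text is not in the protocol, and Figure 1 is not shown. Either may name the right dose. This is a reason to check them, and the Table 2 text would still need correcting.
- **Safeguards.** All notes go to the clinical care team, which makes a lasting under-dose less likely. Still, no stated step requires anyone to confirm the step-down dose. The stated calls to the team follow concerning or worsening symptoms, and a recovered patient has neither.
- **Small scale.** At most five patients are exposed, over about 30 days each, in a phase meant to refine workflows. This stands and limits the weight of the point. However, section 2.2 says that what is learned will inform the final phase 3 process, so an uncorrected line could be carried forward.

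**Conclusion.** The point holds. Table 2 states a step-down dose that does not match its own starting dose or the narrative, and for a patient whose maintenance dose was raised after discharge the literal rule gives the wrong dose.

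The size is limited to at most 5 Phase 1 patients, and among them only those meeting all three conditions. Patients with an unchanged dose are unaffected. The remaining share of 67% or 50% of the maintenance dose rests on assumed raises of 1.5-fold and 2-fold. Nothing is claimed about lowered doses. The discharge dose was itself prescribed and the notes are forwarded, which limits the harm without correcting the rule. The point is worth fixing because it is a dosing instruction and the correction is simple.

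**What to change.** Use one reference dose for both doubling and step-down, in Table 2, the narrative after it and the EPIC template. Suggested wording: *the current standard dose, meaning the dose set at discharge or, if later changed, the most recent maintenance dose set by the heart failure care team*. Check that Figure 1 uses the same term.

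A separate small clarification could go in with the same edit. For patients doubled on 1–4 lb weight gain with device alerts, the narrative speaks of stopping the diuretic once weight normalises. It should say that the doubled dose stops and the standard dose resumes. The conclusion above does not depend on this.

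The cost is protocol and template wording only.

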After discharge, CHF patients will be asked two questions every morning from the pinpoint IQ application. The pinpoint IQ platform will query patients about their current weight and if they actively have symptoms. These symptoms include chest pain, shortness of breath at rest, lightheadedness, dizziness, passing out, lower extremity swelling, orthopnea and postural nocturnal dyspnea. The monitoring nurse will evaluate the pinpoint IQ in the morning after the patient has filled out the questionnaire. They will evaluate the responses to the questions and the physiologic alerting system built by physIQ. There will be an algorithm built within physIQ's system that provides an alert to the monitoring nurse if the criteria from Table 1 are met.

Patients 1-5:
Any positive symptom
Example Question: Do you have any of the following symptoms? (multi-choice)
a. Chest pain b. Shortness of breath at rest c. Lower extremity edema d. Orthopnea (not able to lay flat) e. PND (Waking up in the middle of the night short of breath) f. Syncope (Passing out) g. Fatigue h. Vomiting i. Diarrhea
5 lb weight gain over dry weight (
Example Question:
What is your dry weight? What is your weight today?
A high risk alert
A predefined number of standard alerts in a day + 1-4 lb weight gain over dry weight

Table 1: Phase 1, physIQ alerts system for monitoring nurse for CHF

The actual thresholds for the high-risk alerts and the number of standard alerts may be changed from patient to patient based on how each case progresses and the density and frequency of alerts. Determining the optimal thresholds for these two types of alerts will be a key aim of phase 2. The goal is to maximize signal while minimizing noise.

If any of these conditions listed in Table 1 are met, the monitoring nurse will call the patient and go through a predefined note with the following data elements and questions.

monitoring nurse Alert System – CHF, phase 1

Do you currently have the following symptoms? (y/n)

- **Chest pain**
- **Shortness of breath at rest**
- Lower extremity edema
- Orthopnea (not able to lay flat)
- PND (Waking up in the middle of the night short of breath)
- **Syncope (Passing out)**
- Fatigue
- Vomiting
- Diarrhea

(Any Red Bolded symptoms results in phone call to clinical team and may physically see patients at home)

What is your dry weight? (Can look up patient's discharge weight and fill in or automate with data element)

What is your weight today? (Free text)

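### Section 2.2 ends a doubled diuretic dose by two contradictory rules: symptoms AND weight in Table 2, symptoms OR weight in the text that follows

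*Protocol*

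**What the plan says.** All of this stands in Protocol section 2.2, Phase 1.

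- **Step-down, Table 2 (Diuretic Medication):** "If on double diuretic dose and no longer symptomatic AND back to dry weight, deescalate diuretic dose to discharge dose".
- **Step-down, text after Table 2:** "If symptoms or weight gain normalize, the double dose of diuretic will be deescalated to the standard dosing regimen". The sentence just before it keeps the doubled dose when symptoms have improved or not changed. Worsening symptoms lead to a call to the care team.
- **Exit for 1-4 lb gain plus device alerts, next paragraph:** "we will stop diuretic dosing if weight gain normalizes back to dry weight".
- **Doubling on alerts, Table 2:** a gain of 1-4 lb "with a prespecified number of standard alerts or a high risk alert than ask patient to double diuretic dose". **The same in the text:** "some combination of weight gain and standard alerts or a high-risk alert, then the doubling of diuretics will also occur".
- **Where the rule operates:** "Escalating and deescalating diuretic dosing will also be built into the same note template". Table 2 is the content to be configured as the EPIC note.

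**The concern.** The table and the text govern one action by one nurse, in one note template that is meant to standardize practice, yet they use different logical connectives. Two nurses who follow the protocol faithfully could give the same patient opposite dosing instructions on the same morning.

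Stepping down too early leaves a congested patient on a dose already judged insufficient. Stepping down too late prolongs a doubled diuretic, and the protocol recognizes that risk by requiring a metabolic panel after three days of escalation. Phase 1 also exists to test the workflow, and with two exit rules it is unclear which workflow was tested.

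**Working it through.** The protocol gives no figure to reproduce, so the check sets the two rules side by side. I take weight to have normalized when it is back at dry weight, because the 1-4 lb exit sentence uses the word that way.

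| Patient on doubled dose | Table 2 (AND) | Text after Table 2 (OR) |
|---|---|---|
| Symptoms cleared, at or below dry weight | step down | step down |
| Symptoms cleared, 1-4 lb over | keep | step down |
| Symptoms cleared, 5 lb or more over | keep | step down, with the 5 lb doubling threshold still met |
| Symptoms persist, at or below dry weight | keep | step down by the OR sentence; keep by the sentence before it if symptoms are better or the same |
| Symptoms persist, above dry weight | keep | keep |

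**Rows 2 and 3** are a direct contradiction. The clearest case is a patient who had symptoms that have since resolved: the OR is then satisfied by symptoms alone, whatever the scale shows.

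**Could the OR mean whichever sign opened the doubling?** The text does not say so, and that reading does not remove the conflict. Take a patient doubled for symptoms who is now symptom-free but 3 lb over dry weight. The opening sign has resolved, so the text steps the dose down. Weight is not back to dry weight, so Table 2 keeps it doubled. That reading would bring the two into line only for a symptom-free patient doubled on weight alone.

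**Row 4** is different. The OR sentence conflicts with Table 2, but it also conflicts with the sentence before it, which holds the dose. This is tension within the text as much as between text and table.

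**The 1-4 lb plus alerts route.** Table 2's step-down is not limited by trigger, so it applies here too, and its target is the discharge dose. The text's exit needs weight only, without symptoms, and its literal target is no diuretic.

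**High-risk alert (secondary).** Both doubling sentences parse in two ways:

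- a high-risk alert alone doubles the dose;
- a high-risk alert doubles it only together with weight gain.

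Table 1 lists the high-risk alert on its own line, apart from the line pairing standard alerts with 1-4 lb. That line governs when the nurse is alerted, not when the dose is doubled, so it supports the first reading without settling it. No step-down wording refers to the alert. If an alert alone does double the dose, a symptom-free patient at dry weight already satisfies the substance of Table 2's exit on the day of doubling. Figure 1, the process map for patients 1-5, is not shown and may resolve this.

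**The case against.** The strongest reply is that Table 2 is what the nurse will see in EPIC, so AND is the operating rule and the text is loose narrative. That is plausible, but the protocol states no precedence and says that the escalation and de-escalation it describes are built into the same note. Daily review, forwarding of every note to the clinical team and that team's discretion limit the harm. They do not decide which rule the nurse applies first. Varying alert thresholds between patients, which the protocol allows, does not extend to the choice between AND and OR.

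Other parts of the reply stand, and they rule out stronger readings that a reader might infer:

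- **That nothing ends a doubling made on a high-risk alert alone.** Table 2's step-down covers anyone on a doubled dose, whatever the trigger. What can be said is that no exit refers to the alert and that the trigger itself is ambiguous.
- **That Table 2 orders doubling and step-down at once.** It does not. Its doubling line applies to patients on the standard dose and its step-down line to patients on the doubled dose. Re-doubling at a later assessment is possible, but that is a weaker point.
- **That a recovered patient is never taken through the step-down.** The text says "If any of these conditions listed in Table 1 are met, the monitoring nurse will call the patient and go through a predefined note", but not that the note is used only then. The nurse also reviews responses every morning, and the note offers options for a patient at or below dry weight and for de-escalation.
- **That the protocol intends to withdraw the diuretic.** The doubled dose is probably what is meant by stopping. The fault is that the words say something else.

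**Conclusion.** The point holds and the rule is wrong as written. Table 2 and the text give opposite instructions for a patient whose symptoms have cleared but who remains above dry weight, including one still at or over the 5 lb threshold. For persisting symptoms at dry weight, the OR sentence is at odds with Table 2 and with its own neighbour. The instruction to stop dosing does not match Table 2's return to the discharge dose. The ambiguity over the high-risk alert is real but secondary, and Figure 1 may settle it.

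The scope is the nurse-applied rule for the five Phase 1 patients. Nothing here changes an endpoint, a comparison or the statistical analysis, and the documents do not show how often the conflicting situations would arise. The conclusion assumes that table and text are meant to describe the same action, as the sentence on the shared note template indicates.

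**What to change.** 1. In the text after Table 2, replace the OR condition with: symptoms have resolved AND weight is at or below dry weight. This matches Table 2 and agrees with the sentence that holds the dose while symptoms persist.
2. In the 1-4 lb plus alerts sentence, replace the instruction to stop dosing with a return to the discharge diuretic dose, under the same joint criterion.
3. State in Table 2 and in the text whether a high-risk alert without weight gain doubles the dose.
4. Check that the EPIC note and Figure 1 carry the same single rule.

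I would not add a requirement that the patient be free of high-risk alerts before step-down. That is a clinical trade-off, and it could prolong doubled dosing while alert thresholds are still being tuned.

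The cost is a few sentences in section 2.2 and a check of the template and figure. No extra patients, visits or analyses are needed.

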these providers. There are some standardized workflows that will be followed by the care team that are of note. If the patient has diuretic dose escalated for 3 days, then the clinical care team will make sure patient has a basic metabolic panel ordered to make sure patient's renal function is stable on the higher diuretic dose. We created a standardized note template for mid-level providers as part of the escalation pathway (Table 3). Also, all messaging from the monitoring nurse will be forwarded to the heart failure clinical pool and/or CHF APP pool per protocol to create the most rapid response back to the patient if required.

Cardiovascular symptoms not related to CHF Is the patient having any concerning cardiovascular symptoms not related to CHF? (y/n)
Pulmonary symptoms Is the patient having any concerning pulmonary symptoms not related to CHF? (y/n)
Infectious symptoms Is the patient having any symptoms concerning for an infection (eg: fever, dysuria, productive cough, diarrhea, vomiting, rash, or flu-like symptoms)? (y/n)
Urine output Does the patient have decreased urine output or are they not responding to their diuretic dose? (y/n)
Hematologic symptoms (such as bleeding and thrombosis) Is the patient having any concerning hematologic symptoms? (y/n)
Medication adherence questions 
 • In the last week has the patient missed any diuretic doses (eg: lasix, bumex, spironolactone)? (y/n/na) • In the last week has the patient missed any beta blocker doses (eg: metoprolol, carvedilol)? (y/n/na) • In the last week has the patient missed any ACE/ARB doses (eg: enalapril, lisinopril, benazepril, captopril, quinapril, irbesartan, losartan, olmesartan, valsartan)? (y/n/na)
Self-Care 
 1. Did the patient ask any questions related to self-care? (y/n) 2. Did a family member or caregiver ask any questions related to self-care? (y/n) 3. Did the patient or a family member or caregiver know their medications? (y/n) 4. What led to your communication with the patient? (monitoring nurse recommendation, patient called, abnormal lab finding, other)
Assessment 
 1. What do you think is the cause of the patient's decompensation? (HF exacerbation, cardiovascular non-HF, pulmonary, infectious, renal, other) 2. On a scale of 1 to 5 how confident are you in this choice? 1 being least confident, 5 being extremely confident (select number 1-5 from drop down menu)

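### Protocol section 2.2 gives inconsistent rules for ending the nurse-directed doubled diuretic dose, and no text says which one applies

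*Protocol*

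**What the plan says.** All of the relevant text is in Protocol section 2.2, Phase 1.

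- **Table 2 (monitoring nurse template).** Exit from the double dose: "If on double diuretic dose and no longer symptomatic AND back to dry weight, deescalate diuretic dose to discharge dose". The entry rule in the same table doubles the dose for any of four new congestive symptoms (breathlessness at rest, leg edema, orthopnea, PND), for a gain of 5 lb or more, or for a 1-4 lb gain with device alerts.
- **Narrative after Table 2, general exit.** "If symptoms or weight gain normalize, the double dose of diuretic will be deescalated to the standard dosing regimen".
- **Narrative, the sentence just before.** "If the symptoms are getting better or are the same, the double dose of diuretic will remain unchanged". Worsening symptoms lead to a phone call to the care team.
- **Narrative, 1-4 lb gain plus device alerts only.** "we will stop diuretic dosing if weight gain normalizes back to dry weight". No symptom condition is attached.
- **Status of the template.** "Table 2 will be configured into a note template within EPIC that allows for data elements to be captured", and the narrative adds "Escalating and deescalating diuretic dosing will also be built into the same note template". Neither sentence gives one text precedence over the other.

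**The concern.** These are dose instructions that a nurse carries out by telephone. The template is meant to make that process uniform, which fails if the protocol holds two exit rules. One joins the conditions with a capitalised AND; the other joins them with *or*. Where they differ, the narrative removes the extra diuretic earlier than Table 2 does.

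The *stop* sentence is a separate matter. Table 2 returns the patient to the discharge dose. The narrative, for one pathway, speaks of stopping diuretic dosing. In heart failure, going back to the maintenance dose and giving no diuretic are very different actions.

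Phase 1 is also where workflows are to be finalised (section 2.1), so loose wording here could carry into later phases.

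**Working it through.** The protocol states no figure on this point, so the check compares the rules state by state for a patient already on the double dose. I take weight normalising to mean a return to dry weight.

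**General exit rule.** Table 2 de-escalates if symptoms are resolved AND weight is at dry weight. The narrative, read literally, de-escalates if either holds.

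| Symptoms | Weight | Table 2 | Narrative, literal *or* | Agree? |
|---|---|---|---|---|
| Present | Above dry | Keep double | Keep double | Yes |
| Present | At dry | Keep double | De-escalate | No |
| Resolved | Above dry | Keep double | De-escalate | No |
| Resolved | At dry | De-escalate | De-escalate | Yes |

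Table 2 de-escalates in 1 of 4 states and the literal *or* in 3 of 4, so they differ in 3 − 1 = 2 of 4.

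**The two differing states are not alike.**

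1. *Symptoms present, at dry weight.* The narrative's preceding sentence keeps the double dose while symptoms are better or unchanged, which agrees with Table 2. The conflict here is between two adjacent narrative sentences. It is the same state already counted, not an additional one.
2. *Symptoms resolved, above dry weight.* No other narrative sentence restores agreement. This is the clear departure: 1 of 4 states.

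**Splitting the second state by Table 2's own weight levels.**

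- *5 lb or more:* a patient returned to the standard dose at once meets the entry rule, so the dose would be doubled again.
- *1-4 lb with qualifying device alerts:* the entry rule again doubles the dose.
- *1-4 lb, no symptoms, no qualifying alerts:* Table 2 keeps the double dose and the narrative does not. This difference lasts, although neither text would start a double dose in this state.

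**Other readings of *or*.** If it means whichever trigger was present, the rules differ in 1 of 4 states: symptoms resolved with weight up for a symptom-triggered patient, or symptoms present at dry weight for a weight-triggered patient. If it means every abnormality present must normalise, they differ in 0 of 4. The range is therefore 0 to 2 of 4, and the literal text gives 2.

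**Pathway of 1-4 lb plus alerts.** The narrative exits on weight alone. Without symptoms this matches Table 2's timing (0 of 2 weight states differ). If symptoms can also be present, 1 of 4 states differs (symptoms present, at dry weight). The action differs on the literal text: Table 2 gives the discharge dose, the narrative stops dosing. The nurse's plan list in Table 2 offers escalation, de-escalation and a free-text option, but no stop or hold. A hold option is listed only in Table 3, the mid-level provider template.

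**The case against.** The strongest reply is that the protocol works in practice. The nurse's tool is the EPIC template, and Table 2, from which it is built, carries the explicit AND. The hold sentence covers persisting symptoms. The entry rule re-doubles the dose at 5 lb or more. The care team sees everything: "All notes will be forwarded to the clinical care team". Prolonged escalation is also checked: "If the patient has diuretic dose escalated for 3 days, then the clinical care team will make sure patient has a basic metabolic panel". *Stop* is loose shorthand, since it directly follows text about doubling.

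Much of this stands. It narrows the clear departure to one state and makes the literal *stop* unlikely to be what was meant. It does not remove the inconsistency. Forwarded notes allow review only after the nurse has acted, and the metabolic panel checks renal function on the higher dose, not early withdrawal.

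A reader might infer that the narrative is simply wrong and Table 2 right. The documents do not settle that. No text gives Table 2 precedence, and Figure 1, the process map for these patients, is not shown in the reviewed copy. Nor is Table 2's wording safe to copy unchanged. Its symptom list includes fatigue, vomiting and diarrhea, which do not trigger doubling. An unqualified requirement to be symptom-free could hold a patient with vomiting or diarrhea, already at dry weight, on a doubled diuretic.

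**Conclusion.** The inconsistency is real and stands in current text. The general exit rules differ in 2 of 4 states on the literal wording. One of those is a clear departure from Table 2 (symptoms resolved, weight still up). The other is a contradiction within the narrative that its own hold sentence resolves in Table 2's favour. The *stop* sentence is a separate wording fault confined to the 1-4 lb plus alerts pathway.

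Two stronger readings go too far. One is that the protocol withdraws all diuretic from every patient leaving the double dose: the sentence covers one pathway and probably means the extra dose. The other is that patient care or results would demonstrably change: the counts above are of states, not patients, and the protocol does not say how many of the 5 Phase 1 patients would reach each. No endpoint or analysis is shown to be affected.

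Priority is minor to should-fix, as safety wording. The conclusion rests on the quoted text and on reading normalised weight as dry weight.

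**What to change.** Write one exit rule and use it everywhere. For example: once the congestive symptoms that trigger doubling (orthopnea, PND, leg edema, breathlessness at rest) have resolved AND weight is at or below dry weight, return to the discharge (standard) diuretic dose. If the heart failure team prefers a different single rule, use that one.

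- Replace the narrative's *or* sentence with this rule.
- Replace the *stop* wording for the 1-4 lb plus alerts pathway with return to the discharge (standard) dose under the same rule.
- In Table 2 and the EPIC template, specify which symptoms count for the exit.
- Check that Figure 1 shows the same rule.

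The cost is a few wording edits, a check of the figure and template, and confirmation by the heart failure team. No visits, procedures or patients are added.
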